1.5. Risk/Benefit Assessment for the Study

Potential risks of a participant's study involvement include unknown adverse events (AEs), general risks associated with frequent clinic visits and laboratory blood draws, local events of injection including site pain, swelling, and erythema, as well as systemic events of fatigue, fever, arthralgia, myalgia, headache, and nausea. Strategies to mitigate these risks include close monitoring of participants' clinical status, laboratory values, and AEs in the immediate postdose period and beyond. Parameters for discontinuation of the investigational product due to AEs will be well defined and closely followed.

This is a first-in-human study and there may be unknown risks associated with the investigational product. This may include allergic and hypersensitivity reactions and/or anaphylaxis, which have been observed in similar vaccines. Due to these risks, sentinel participants will be observed at the study site for at least 8 hours after investigational product administration on Day 1, and for at least 4 hours following each administration of investigational product for all subsequent doses. All other Phase 1a participants will be monitored in the clinic for at least 4 hours following each dose of investigational product. Participants in Cohorts 5, 6, and 7 will be monitored in the clinic for at least 2 hours following each dose of investigational product. Participants may be required to remain in the clinic for additional observation at the discretion of the investigator. Participants who experience hypersensitivity or anaphylaxis will discontinue the investigational product and will not be rechallenged. The duration of the monitoring period may be revised based on recommendations of the Safety Review Team (SRT).

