This stepwise, gated approach will mitigate any unknown risks of dose-level increases, and the additional dose of alternating 2-vector therapy. Based on the current information (included in the IB), it is anticipated that the overall benefit-risk profile is comparable between 2 versus 3 doses of 2-vector combination therapy in healthy participants, and participants with CHB.

Immune-mediated conditions have been reported in some studies and in clinical use of some vaccines. In this early-stage protocol, individuals with a history of autoimmune diseases are excluded. Investigational product will be stopped for any participant with a new onset or worsening of any potentially immune-mediated condition, regardless of assessment of relationship to study vaccination. Management of such events will be based on the best available local standard of care. A list of potential immune-mediated conditions is provided in Appendix 11.7.

The investigational product has induced HBV-specific immune responses in nonhuman primate studies indicating a potential to mediate functional cure in individuals with CHB. There is however no clinical data suggesting any known direct benefit to participants in this study. The data from this study will, however, support the development of GS-2829 and GS-6779, products that when used in combination therapy could help achieve a curative treatment for HBV.

An infectious disease pandemic may pose additional risks to investigational product availability, study visit schedule, and adherence to protocol-specified safety- monitoring or laboratory assessments. Refer to Appendix [11.3](#) for further details on the risks and risk mitigation strategy.

Considering the above, the benefit-risk balance for this study is considered positive.

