3.3. Protocol-Specific Discontinuation Criteria

GS-2829 and GS-6779 have been evaluated in nonclinical studies without any identified dose-limiting toxicity up to the highest proposed dose. In this first in human protocol, the following rules will guide early discontinuations from the study.

3.3.1. Criteria for Early Discontinuation for the Individual Participant From the Investigational Product

Administration of the investigational product should be discontinued in the following instances:

- If a participant experiences a Grade 3 or higher treatment-emergent AE (TEAE; excluding nausea, headache, measured grades of erythema and edema/induration alone) or confirmed Grade 3 or higher laboratory abnormality (except for those with a physiologic explanation for the events [eg, blood in urine occurring in a menstruating female, creatine phosphokinase elevation after strenuous exercise, triglyceride elevation that is nonfasting, etc]) considered clinically significant by the investigator and judged as related to the investigational product
- Any AE, laboratory abnormality or intercurrent illness which, in the opinion of the investigator, indicates that continued participation in the study is not in the best interest of the participant
- Participant request to discontinue for any reason
- Participant noncompliance
- Pregnancy during the study (refer to Appendix [11.4](#))
- Loss to follow-up
- Investigator discretion
- Discontinuation of the study by the sponsor

If a participant refuses to receive the remaining doses of investigational product as the result of an AE that is judged by the investigator as related to investigational product, an early termination (ET) visit should be completed, and every attempt should be made to retain the participant in the study to continue study evaluations. Following the receipt of any abnormal results believed to be related to investigational product at the ET visit, further testing should be repeated weekly or as often as deemed clinically appropriate by the investigator until the abnormality resolves, returns to baseline visit levels, or is otherwise explained.

If the participant withdraws consent from the study, the ET evaluations and/or procedures should be performed within 7 days of the decision to discontinue from the study.

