7.7. Toxicity Management

All treatment-emergent toxicities will be noted by the investigator and brought to the attention of the Gilead medical monitor, and the appropriate course of action will be discussed and decided. Whether or not considered treatment-related, all participants experiencing AEs must be monitored periodically until symptoms subside, any abnormal laboratory values have resolved or returned to baseline levels or they are considered irreversible, or until there is a satisfactory explanation for the changes observed.

Any questions regarding toxicity management should be directed to the Gilead medical monitor.

All clinical and clinically significant laboratory toxicities will be managed according to uniform guidelines detailed in Appendix 11.5, and as outlined below.

- Grade 3 or 4 clinically significant laboratory abnormalities should be confirmed by repeat testing as soon as possible, and preferably within 3 calendar days after receipt of the original test results. The investigational product may be continued without dose interruption for a clinically insignificant Grade 3 and 4 laboratory abnormality (eg, CK elevation after strenuous exercise, triglyceride elevation that is nonfasting or that can be medically managed). Recurrence of laboratory abnormalities considered unrelated to the investigational product may not require permanent discontinuation.
- Grade 3 or 4 clinical events, if considered unrelated to the investigational product, may not require dose interruption and continuation of the investigational product is at the discretion of the investigator.

The Gilead medical monitor should be consulted prior to investigational product discontinuation when medically feasible.

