7.7.1. Grades 1 and 2 Laboratory Abnormality or Clinical Event

- For a Grade 1 or 2 clinical event or clinically significant laboratory abnormality, continue the investigational product at the discretion of the investigator.

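### The mandatory stops in Protocol Section 1.5 for immune-mediated conditions and hypersensitivity are not carried into the sections that govern dosing, and Section 7.7.2 conflicts with them

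*Protocol*

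**What the plan says.** Protocol Section 1.5 sets two stops for the individual participant.

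- Potential immune-mediated conditions (PIMMCs): "Investigational product will be stopped for any participant with a new onset or worsening of any potentially immune-mediated condition", and this applies "regardless of assessment of relationship to study vaccination". Appendix 11.7 lists the conditions.
- Hypersensitivity: "Participants who experience hypersensitivity or anaphylaxis will discontinue the investigational product and will not be rechallenged".

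The same section promises that "Parameters for discontinuation of the investigational product due to AEs will be well defined and closely followed", and it refers the reader to Section 3 for the stopping rules.

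The sections that govern dosing read differently.

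- Section 3.3.1 names neither event. Its adverse event criterion opens "If a participant experiences a Grade 3 or higher treatment-emergent AE" and ends "considered clinically significant by the investigator and judged as related to the investigational product". Its remaining routes for an adverse event are investigator opinion and investigator discretion.
- Section 7.7: "Grade 3 or 4 clinical events, if considered unrelated to the investigational product, may not require dose interruption".
- Section 7.7.1: "For a Grade 1 or 2 clinical event or clinically significant laboratory abnormality, continue the investigational product at the discretion of the investigator".
- Section 7.7.2 has related Grade 3 events withheld until they fall to Grade 2 or lower, ALT and AST elevations excepted.
- Section 7.7.3 permanently discontinues for related Grade 4 events.
- Section 7.7.5, the section devoted to PIMMCs, asks for them to be reported at any grade and says nothing about dosing.

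**The concern.** This is a first-in-human vector vaccine given as 2, 4 or 6 injections, so after a reaction the site usually has to decide whether to give the next one. A site that follows Section 1.5's own pointer goes to Section 3, and from there to the toxicity rules in Section 7.7. In neither place does it meet either stop. It could then re-dose, in good faith, a participant whom Section 1.5 says must receive no more product.

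The PIMMC stop is also incomplete as written. Section 1.5 says only that product is stopped. Table 11 in Section 7.7.4 treats a stop with possible restart and a permanent discontinuation as separate actions, so sites could apply the PIMMC stop differently. Phase 1b alone plans about 15 sites. The SAP does not settle the matter: its Section 7.1.8 tabulates hypersensitivity and immune-mediated events but contains no dosing rule.

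**Working it through.** No arithmetic applies. The check takes specific cases through Section 1.5 and then through the dosing sections.

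1. **A Grade 1 or 2 PIMMC**, for example a mild Bell's palsy, which Appendix 11.7 lists. Section 1.5: stop. Section 3.3.1: the Grade 3 criterion is not met, so only the investigator-judgment routes remain. Section 7.7.1: product may continue at the investigator's discretion. Section 7.7.5: report.
2. **A Grade 3 or 4 PIMMC judged unrelated.** Section 1.5: stop, because relatedness does not matter. Section 3.3.1: not met, because the criterion requires a related event. Section 7.7: continuation is left to the investigator.
3. **A Grade 1 or 2 hypersensitivity reaction to the product.** Section 1.5: discontinue, no rechallenge. Section 7.7.1: product may continue at discretion.
4. **A Grade 3 hypersensitivity reaction to the product.** Section 1.5: discontinue, no rechallenge. Section 3.3.1: discontinue, if the event is clinically significant. Section 7.7.2: withhold, then resume once the event is Grade 2 or lower. Section 7.7.2 therefore conflicts with both of the other sections.
5. **A related Grade 4 event of either kind.** Sections 1.5, 3.3.1 and 7.7.3 all end dosing. There is no gap.

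Case 2 depends on how Section 3.3.1 is read. The closing condition on significance and relatedness is taken here to cover clinical events as well as laboratory abnormalities, which fits Section 7.7. If it covers laboratory abnormalities only, Section 3.3.1 would discontinue for unrelated Grade 3 or higher clinical events too, apart from its listed exclusions, and would then contradict Section 7.7. Cases 1, 3 and 4 do not depend on this reading.

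Case 3 depends on how the hypersensitivity rule is read. Section 1.5 introduces it among the possible risks of the product, and a bar on rechallenge makes sense only for a reaction to the product. An unrelated seasonal or food allergy is therefore taken to be outside the rule.

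**The case against.** The strongest reply is that nothing is missing. Both stops are in the protocol in mandatory terms, and Sections 1.6 and 9.1.9 require the study to follow the protocol. A specific mandatory rule can stand beside general discretion, and a site can obey Section 1.5 without breaching Section 7.7 or 7.7.1.

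There are also partial safeguards:

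- Section 7.7 brings all treatment-emergent toxicities to the medical monitor.
- Section 3.3.1 lets the investigator discontinue for any adverse event, of any grade, in the participant's interest.
- Section 6.2 requires continuing eligibility, and the exclusion criteria cover autoimmune disease and known hypersensitivity to the product, although they are framed as screening criteria.
- Section 7.7.4 holds dosing for defined liver-test elevations in Cohorts 1 to 4 and 8, and Table 11 recommends a stop or permanent discontinuation at set thresholds in Cohorts 5 to 7. Neither asks about relatedness.

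Much of this stands. It rules out the inference that the protocol has no stop for these events. It does not remove the point: none of these safeguards states the two stops, Section 1.5 itself sends the reader to Section 3 for the rules, and the conflict in Section 7.7.2 is direct.

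A reader might also infer that Table 11 tells sites to keep dosing in autoimmune hepatitis, because one row continues product for persistent enzyme elevation and makes no immune-mediated exception. That row manages an enzyme pattern, not a diagnosis. Once an immune-mediated cause is diagnosed, Section 1.5 applies. A cross-reference would help, but the row is not itself an error.

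**Conclusion.** The point holds as an internal inconsistency in a participant-safety rule and should be fixed. Its clearest instances are Grade 1 or 2 PIMMCs, Grade 1 or 2 hypersensitivity reactions to the product, and related Grade 3 hypersensitivity under Section 7.7.2. Unrelated Grade 3 or 4 PIMMCs belong with them on the natural reading of Section 3.3.1.

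No numerical size is claimed. A reader might tabulate grade against relatedness and count the combinations without a mandatory stop outside Section 1.5. The documents do not support such a count: the liver-test rules reach some unrelated events, and Section 7.7 refers to guidelines in Appendix 11.5 whose content is not visible here and might repeat either stop. A reader might also offer the number of planned repeat injections as the size. That number does not measure the defect: the documents give no event rate, and because the vectors alternate in Cohorts 3 to 8, some of those injections are a first dose of the second vector.

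The conclusion assumes that the hypersensitivity rule means reactions to the product, and that Appendix 11.5 does not already resolve the conflict.

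**What to change.** Add two criteria to Section 3.3.1:

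- (a) Stop product for any new or worsening PIMMC in Appendix 11.7, at any grade and whether or not related. The sponsor should state whether the stop is permanent or on what terms dosing may restart.
- (b) Permanently discontinue, without rechallenge, for hypersensitivity or anaphylaxis to the product at any grade.

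Then:

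- State both as exceptions to Sections 7.7, 7.7.1 and 7.7.2.
- Put the dosing action for (a) in Section 7.7.5.
- Note in Table 11 that a diagnosed immune-mediated cause follows (a).
- Align Section 7.7.2 with Section 3.3.1 for related Grade 3 events, and check that Appendix 11.5 agrees.

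The cost is a few sentences in a protocol amendment, with no new assessments. Some participants with mild or unrelated events will lose later doses, but Section 1.5 already requires that. For PIMMCs, how many doses are lost depends on whether the sponsor makes the stop permanent.

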1.6. Compliance

This study will be conducted in compliance with this protocol and in accordance with the ethical principles that have their origin in the Declaration of Helsinki and that are consistent with International Council for Harmonisation (ICH) Good Clinical Practice (GCP) and applicable regulatory requirements.

2. OBJECTIVES AND ENDPOINTS

The study objectives and endpoints are outlined in [Table 7](#).

Table 7. Study Objectives and Endpoints

Primary Objective	Primary Endpoint

To evaluate the safety and tolerability of repeated dosing of GS-2829 and GS-6779 in healthy participants and in virally suppressed participants with CHB	
Proportion of participants with treatment-emergent AEs, SAEs, and laboratory abnormalities
Secondary Objective	Secondary Endpoints

To evaluate the immunogenicity of repeated dosing of GS-2829 and GS-6779 in healthy participants and in virally suppressed participants with CHB	
Incidence and magnitude of vaccine-induced T-cell responses
Exploratory Objectives	Exploratory Endpoints

To further evaluate the T- and B-cell immunogenicity and mechanism of action of GS-2829 and GS-6779 in healthy participants and in virally suppressed participants with CHB	
Postvaccination changes in T-cell subset frequencies and activation status from baseline levelsPostvaccination changes in HBV-specific B-cell subset frequencies from baseline levelsPostvaccination changes in HBV antigen-antibody immune complexes from baseline levelsPostvaccination changes in HBV-specific antibodies from baseline levelsPostvaccination changes in HBV-specific neutralizing antibodies from baseline levels

To evaluate the impact of GS-2829 and GS-6779 on HBV-specific viral biomarkers in participants with CHB	
Change in HBsAg from baselineProportion of participants with HBsAg loss with or without HBsAg seroconversionChanges in quantitative HBV RNA, HBV DNA, hepatitis B core-related antigen (HBcrAg), hepatitis B e antigen (HBeAg), and other HBV viral biomarkers from baselineGenomic sequencing of HBV in virally suppressed participants as needed

To characterize the relationship between immunologic changes and circulating HBV viral markers	
Correlation between changes in immunological biomarkers and circulating HBV viral markers from baseline

To evaluate the presence of antivector antibodies and their impact on immunogenicity and virologic endpoints	
Postvaccination changes in vector-specific antibodies from baseline levels

3. STUDY DESIGN

3.1. Study Design

This protocol describes a blinded, placebo-controlled, randomized Phase 1a and Phase 1b study to evaluate the safety, tolerability, and immunogenicity of repeated doses of GS-2829 and GS-6779 in healthy participants (Phase 1a) and participants with CHB (Phase 1b). The study will comprise 8 cohorts, which will enroll approximately 10 participants each, with a 4:1 randomization either active viral vectors GS-2829 and/or GS-6779 or PBO. The dosing schedules by cohort are provided in [Table 8](#).

Healthy participants aged 18 through 60 years will be enrolled into the Phase 1a part of the study; and participants with CHB aged 18 through 65 years will be enrolled into the Phase 1b part of the study. To ensure there is enough information to assess any differential for safety and tolerability by sex at birth, enrollment of participants of both sexes is encouraged.

An overview of the study design is described below and shown in [Figure 1](#), [Figure 2](#), and [Figure 3](#).

The investigational products GS-2829 and GS-6779 are available as $\geq 1.0 \times 10^7$ FFU/mL. There are 2 dose levels in this study: high dose (0.5 mL of the undiluted solution) and low dose (0.5 mL of the 10-fold dilution of the high dose).

Phase 1a activities will be performed in healthy participants at a single study site. Healthy participants will be enrolled into 1 of 5 cohorts to receive the investigational product as follows:

- Cohort 1 – Single low dose of GS-2829 or PBO on Day 1 and Day 57.
- Cohort 2 – Single low dose of GS-6779 or PBO on Day 1 and Day 57.
- Cohort 3 – Single low dose of GS-2829 or PBO on Day 1 and Day 57; and single low dose of GS-6779 or PBO on Day 29 and Day 85.
- Cohort 4 – Single high dose of GS-2829 or PBO on Day 1 and Day 57; and single high dose of GS-6779 or PBO on Day 29 and Day 85.
- Cohort 8 – Single high dose of GS-2829 or PBO on Day 1, Day 57, and Day 113; and single high dose of GS-6779 or PBO on Day 29, Day 85, and Day 141.

Phase 1b activities will be performed at multiple study sites (approximately 15) in participants diagnosed with CHB who are virally suppressed (Cohort 5, 6, and 7). These participants will be enrolled into 1 of 3 cohorts to receive the investigational product as follows:

- Cohort 5 – Single low dose of GS-2829 or PBO on Day 1 and Day 57; and single low dose of GS-6779 or PBO on Day 29 and Day 85.

- Cohort 6 – Single high dose of GS-2829 or PBO on Day 1 and Day 57; and single high dose of GS-6779 or PBO on Day 29 and Day 85.
- Cohort 7 - Single high dose of GS-2829 or PBO on Day 1, Day 57 and Day 113; and single high dose of GS-6779 or PBO on Day 29, Day 85, and Day 141.

Cohorts 1, 2, and 3

Cohorts 1 and 2 will enroll concurrently and will receive investigational product in 2 groups, a sentinel group (2 active and 1 PBO, randomly assigned) and the remainder (6 active and 1 PBO), for a total of approximately 10 healthy participants per cohort. Dosing the remainder of Cohorts 1 and 2 and initiation of Cohort 3 will commence at the discretion of the investigator in consultation with the sponsor's medical monitor upon evaluation of available safety data through at least 14 days after the first dose of investigational product in Cohort 1 and 2 sentinel participants. The duration of this review period may be increased based on emerging preliminary safety data. Decisions to initiate a higher dose level cohort and any required revisions to postdose monitoring will be made upon the review of all available safety data by the SRT.

Cohorts 4 and 5

Initiation of Cohorts 4 and 5, which will run concurrently, will be determined at the discretion of the SRT based on the evaluation of available safety data through Day 43 (14 Days after the initial dose of both investigational products for all participants enrolled in Cohort 3), in addition to all available safety data from Cohorts 1 and 2. The decision on cohort initiation will be based on prespecified criteria agreed upon by the SRT and documented in the SRT charter. The duration of this review period may be increased based on the emerging and cumulative safety data.

Cohort 8

Initiation of Cohort 8 will be determined at the discretion of the SRT based on the evaluation of available safety data through Day 43 (14 days after all participants in Cohort 3 have completed the initial dose of both investigational products), in addition to all available safety data from prior cohorts. Initiation of a third dose of 2-vector combination therapy will be determined at the discretion of the SRT based on the evaluation of the available safety data through Day 99 (14 days after all participants in Cohort 4 have completed the second dose of both investigational products), in addition to all available safety data. The decision on cohort initiation will be based on prespecified criteria agreed upon by the SRT and documented in the SRT charter. The duration of this review period may be increased based on the emerging and cumulative safety data.

Cohort 6

Initiation of Cohort 6 will be determined at the discretion of the SRT based on the evaluation of available safety data through Day 43 (14 days after initial dose of both the investigational products for all participants enrolled in Cohort 4), available safety data from participants enrolled

in Cohort 5, and all available safety data from all dosed cohorts, and dosing will be initiated only in the absence of dose-limiting toxicity and/or meeting any prespecified stopping criteria. The duration of this review period may be increased based on the emerging and cumulative safety data.

Cohort 7

Initiation of Cohort 7 will be determined at the discretion of the SRT based on the evaluation of available safety data through Day 43 (14 days after initial dose of both the investigational products for all participants enrolled in Cohort 4), available safety data from participants enrolled in Cohort 5, and all available safety data from all dosed cohorts. Initiation of the third dose of 2-vector combination therapy will be determined at the discretion of SRT based on the evaluation of the available safety data through Day 99 (14 days after all participants in Cohort 4 have completed the second dose of both investigational products), in addition to all available safety data. The decision on cohort initiation will be based on prespecified criteria agreed upon by the SRT and documented in the SRT charter. The duration of this review period may be increased based on the emerging and cumulative safety data.

